5.4 Occurrence of adverse drug reactions/infections by age group

(1) Analysis sets to be used

Safety analysis set, safety analysis set (Hodgkin's lymphoma), and safety analysis set (anaplastic large-cell lymphoma)

(2) Data to be analyzed

The similar calculation as the one described in Section 5.1.2, will be performed by age group (<18 years, 18 to 64 years, 65 to 74 years, or ≥ 75 years).

The type of adverse drug reactions, etc., will be analyzed in the same manner as described in Section 5.1.

(3) Figure/table number

Tables 5.4-1 to 5.4-3

5.5 Occurrence of adverse drug reactions/infections by presence or absence and grade of concurrent hepatic disorder

(1) Analysis sets to be used

Safety analysis set, safety analysis set (Hodgkin's lymphoma), and safety analysis set (anaplastic large-cell lymphoma)

(2) Data to be analyzed

The similar calculation as the one described in Section 5.1.2, will be performed by presence or absence and grade of concurrent hepatic disorder.

The type of adverse drug reactions, etc., will be analyzed in the same manner as described in Section 5.1.

(3) Figure/table number

Tables 5.5-1 to 5.5-3

5.6 Occurrence of adverse drug reactions/infections by presence or absence and grade of concurrent renal disorder

(1) Analysis sets to be used

Safety analysis set, safety analysis set (Hodgkin's lymphoma), and safety analysis set (anaplastic large-cell lymphoma)

(2) Data to be analyzed

The similar calculation as the one described in Section 5.1.2, will be performed by presence or absence and grade of concurrent renal disorder

The type of adverse drug reactions, etc., will be analyzed in the same manner as described in Section 5.1.

(3) Figure/table number

Tables 5.6-1 to 5.6-3

5.7 Occurrence of serious adverse events

(1) Analysis sets to be used

Safety analysis set, safety analysis set (Hodgkin’s lymphoma), and safety analysis set (anaplastic large-cell lymphoma)

(2) Data to be analyzed

Data listed below will be analyzed.

Data item	Data to be analyzed
Number of patients with serious adverse events	Number of patients experiencing serious adverse events
Number of serious adverse events	Number of serious adverse events observed If the same patient has multiple occurrences of the same serious adverse event (PT), the total number of occurrences will be calculated.
Percentage of patients with serious adverse events	Is calculated using the following formula: number of patients with serious adverse events/number of patients included in the safety analysis set × 100.
Type of serious adverse events	The incidence of serious adverse events will be calculated by SOC and PT. For SOC, the number and percentage of patients with serious adverse events will be calculated. For PT, the number and percentage of serious adverse events will be calculated. SOCs will be presented in the internationally agreed order, and PTs will be presented in ascending order of HLGT and PT codes if their SOCs are “Investigations,” and in ascending order of PT code otherwise. If the same patient has multiple occurrences of the same serious adverse event (PT), the event will be counted once per patient. For serious adverse events considered not related to Adcetris, the number of these events will be presented in ().

(3) Figure/table number

Tables 5.7-1 to 5.7-3

5.8 Change in test data over time

5.8.1 Change in laboratory test results over time

(1) Analysis sets to be used

Safety analysis set, safety analysis set (Hodgkin's lymphoma), and safety analysis set (anaplastic large-cell lymphoma)

(2) Data to be analyzed

Summary statistics of red blood cell count, hemoglobin level, white blood cell count, neutrophil count, lymphocyte count, platelet count, total bilirubin, AST, ALT, LDH, BUN, and serum creatinine will be calculated at each test time point [at baseline, after 1 cycle, ... and after 15 cycles]. In addition, box plots of hemoglobin level, neutrophil count, lymphocyte count, and platelet count will be generated at each test time point.

(3) Figure/table number

Tables 5.8.1-1 to 5.8.1-3 and Figures 5.8.1-1 to 5.8.1-3

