#### 10.4.3 Changes in laboratory test data over time

Summary statistics of laboratory test values at baseline and post-baseline will be calculated.

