Days from the date of the last dose of Adcetris to hematopoietic stem cell transplantation (homologous) (Post-baseline hematopoietic stem cell transplantation: homologous)	For patients with post-baseline hematopoietic stem cell transplantation (homologous), this data item will be calculated using the following formula: date of hematopoietic stem cell transplantation (homologous) – date of the last dose of Adcetris + 1. If the date of post-baseline hematopoietic stem cell transplantation (homologous) is missing, this data item should be handled as missing. For patients with no post-baseline hematopoietic stem cell transplantation (homologous), this data item should be handled as missing.
Duration of treatment with Adcetris prior to hematopoietic stem cell transplantation (homologous) (Post-baseline hematopoietic stem cell transplantation: stem cell transplantation: homologous)	For patients with post-baseline hematopoietic stem cell transplantation (homologous), this data item will be calculated using the following formula: date of the last dose of Adcetris – date of the initial dose of Adcetris + 1. If the date of post-baseline hematopoietic stem cell transplantation (homologous) is missing, this data item should be handled as missing.

Term	Definition
homologous)	For patients with no post-baseline hematopoietic stem cell transplantation (homologous), this data item should be handled as missing.
Date of the final observation	“Date of the final observation” in the case report form If not provided, the most recent date entered in the case report form should be used.
Summary statistics	Number of patients, mean, standard deviation, minimum, 25th percentile, median, 75th percentile, and maximum.
Overall survival	Time to the date of death from any cause after the date of the initial dose of Adcetris. Surviving patients will be censored on the date of survival confirmation. The date of outcome of an adverse event with “Died/fetal” recorded in the Outcome field will be used as the date of death, and the final observation date will be used as the date of survival confirmation. The overall survival (date of death or survival confirmation) = date of death or survival confirmation – date of the initial dose of Adcetris+1
1 year	One year is defined as 365.25 days.
1 month	One month is defined as 30.4375 days.

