After 11 cycles	
 • If Cycle 12 is initiated: Date of Cycle 12 • If Cycle 12 is not initiated: 21 days after the date of Cycle 11 	
 • If Cycle 12 is initiated: From the day after the date of Cycle 11 to the day of Cycle 12 • If Cycle 12 is not initiated: From the day after the date of Cycle 11 to 21 days after the date of Cycle 11
After 12 cycles	
 • If Cycle 13 is initiated: Date of Cycle 13 • If Cycle 13 is not initiated: 21 days after the date of Cycle 12 	
 • If Cycle 13 is initiated: From the day after the date of Cycle 12 to the day of Cycle 13 • If Cycle 13 is not initiated: From the day after the date of Cycle 12 to 21 days after the date of Cycle 12
After 13 cycles	
 • If Cycle 14 is initiated: Date of Cycle 14 • If Cycle 14 is not initiated: 21 days after the date of Cycle 13 	
 • If Cycle 14 is initiated: From the day after the date of Cycle 13 to the day of Cycle 14 • If Cycle 14 is not initiated: From the day after the date of Cycle 13 to 21 days after the date of Cycle 13

Time point for testing	Date of protocol-specified assessment	Acceptable time window
After 14 cycles	
 • If Cycle 15 is initiated: Date of Cycle 15 • If Cycle 15 is not initiated: 21 days after the date of Cycle 14 	
 • If Cycle 15 is initiated: From the day after the date of Cycle 14 to the day of Cycle 15 • If Cycle 15 is not initiated: From the day after the date of Cycle 14 to 21 days after the date of Cycle 14
After 15 cycles	
 • If Cycle 16 is initiated: Date of Cycle 16 • If Cycle 16 is not initiated: 21 days after the date of Cycle 15 	
 • If Cycle 16 is initiated: From the day after the date of Cycle 15 to the day of Cycle 16 • If Cycle 16 is not initiated: From the day after the date of Cycle 15 to 21 days after the date of Cycle 15

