1.5 Handling of missing data

- As a general rule, missing data will not be imputed.
- In the analysis of the frequency qualitative variables, missing data will be handles as “unknown.” In the analysis of summary statistics of quantitative variables, missing data will be excluded.

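### SAP 5.8.1 is headed as change over time but calculates no within-patient change, so selective drop-out can distort the apparent laboratory trend in either direction

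*SAP*

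**What the plan says.** The section is headed "5.8.1 Change in laboratory test results over time". For twelve laboratory parameters it specifies summary statistics up to "serum creatinine will be calculated at each test time point [at baseline, after 1 cycle, ... and after 15 cycles". For four of them it adds a display: "box plots of hemoglobin level, neutrophil count, lymphocyte count, and platelet count will be generated at each test time point".

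The definitions in SAP section 1 fix what summary statistics are: "Number of patients, mean, standard deviation, minimum, 25th percentile, median, 75th percentile, and maximum". The count is therefore shown at each time point, but no difference from baseline is.

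SAP 1.5 settles who is in each column: "As a general rule, missing data will not be imputed", and "In the analysis of summary statistics of quantitative variables, missing data will be excluded".

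SAP 1.4 ties the windows to cycle dates. A patient who stops can still supply a value for a limited time after the last dose. For the last time point the assessment date is set as "If Cycle 16 is not initiated: 21 days after the date of Cycle 15", and the window closes on that day. The patient is then absent from all later columns.

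Protocol 10.4.3 also has a heading about changes over time, but its one sentence reads: "Summary statistics of laboratory test values at baseline and post-baseline will be calculated".

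No paired change in a laboratory value is specified in the final SAP, the earlier SAP versions in the same file or the two supplements.

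**The concern.** Each column of the 5.8.1 tables describes a different and generally smaller group than the one before. If staying on treatment is related to the laboratory value, the column means move even when no patient's value does. Loss of patients with low counts would look like recovery. Loss of patients with good counts, or an opposing real change, could look like decline or hide one. The same applies to AST, ALT, LDH and creatinine.

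A link between counts and staying on treatment is plausible here. Protocol 9.2.5 presents control of the neutrophil count as a condition for continuing treatment, and SAP 5.9.8 lists discontinuation among the actions taken for neutropenia. What is at stake is any sentence in the final report that describes how laboratory values changed under Adcetris, because 5.8.1 is the output such a sentence would cite.

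**Working it through.** The plan has no numerical claim about this output. Its one design calculation is in Protocol 3.2: 140 patients give at least 10 infusion reactions at an 11% rate with 95% probability. This reproduces exactly (binomial probability 0.952, smallest n = 140) but has no bearing on 5.8.1.

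The documents give no discontinuation rates and no distribution of counts, so every input below is an assumption.

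**Illustration 1: no patient changes.** Baseline neutrophils are normal with mean 4,000/mm³ and SD 2,000.

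- Mean above and below the median: 4,000 ± 2,000 × √(2/π) = 5,596 and 2,404.
- Mean of those retained = (a × 5,596 + b × 2,404)/(a + b), where a and b are the proportions retained above and below the median.

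| Retained above / below median | Calculation | Reported mean | Apparent change |
|---|---|---|---|
| 60% / 60% | (0.60 × 5,596 + 0.60 × 2,404)/1.20 | 4,000 | 0 |
| 60% / 45% | (0.60 × 5,596 + 0.45 × 2,404)/1.05 | 4,228 | +228 (+6%) |
| 60% / 30% | (0.60 × 5,596 + 0.30 × 2,404)/0.90 | 4,532 | +532 (+13%) |
| 30% / 60% | (0.30 × 5,596 + 0.60 × 2,404)/0.90 | 3,468 | −532 (−13%) |

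In every row the paired change is zero. The paired patients' baseline mean equals the reported mean, so setting it beside the full baseline mean of 4,000 would show the selection directly.

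**Illustration 2: stopping per cycle.** Of 140 patients, 42 stay at 1,000/mm³ and 98 at 3,000/mm³, so the mean after cycle 1 is (42 × 1,000 + 98 × 3,000)/140 = 2,400. The high group stops at 5% per cycle. After cycle 15 the groups number 42 × (1 − h)^14 and 98 × 0.95^14, where h is the low group's stopping rate.

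| h per cycle | n after cycle 15 | Mean after cycle 15 | Apparent change |
|---|---|---|---|
| 5% | 68.3 | 2,400 | 0 |
| 10% | 57.4 | 2,665 | +265 (+11%) |
| 15% | 52.1 | 2,834 | +434 (+18%) |
| 25% | 48.5 | 2,969 | +569 (+24%) |

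**Illustration 3: does paired change repair it?** This is a simulation of 140 patients with 2,000 replicates. Baseline has mean 3,500 and SD 1,200, and each patient has a sustained fall averaging about 1,000. Stopping is 5% per cycle, or the rate shown if the on-treatment level is below 1,500/mm³.

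| Stopping rate if low | Drift in raw mean, cycle 1 to 15 | Paired change, cycle 1 to 15 | Drift in paired change |
|---|---|---|---|
| 5% | +4 | −978 to −976 | 2 |
| 10% | +237 | −976 to −935 | 41 |
| 15% | +370 | −976 to −913 | 63 |
| 25% | +477 | −976 to −898 | 78 |

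Pairing removes most of the drift but not all of it. Patients whose counts fell furthest are more likely to leave, so those who remain also have slightly smaller falls.

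**Window selection.** Under SAP 1.4, when a window holds several values the one nearest the assessment date is used. That date is the next cycle's date when there is one. The window after cycle 1 is that single date. Low values within a cycle will therefore usually not enter 5.8.1, which is a separate reason for a worst-value table.

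**The case against.** The strongest reply is that 5.8.1 is descriptive, delivers what the protocol sentence asks for and more, and plans no test or claim of recovery. That stands: a reader might infer a departure from Protocol 10.4.3, but only the protocol's heading speaks of change.

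A reader might also infer that low neutrophil counts disappear when patients stop. The documents do not support that.

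- SAP 5.9.7 tabulates worst grade of related neutropenia, once per patient, by degree of baseline neutrophil decrease. SAP 5.1.1 recodes reported decreased neutrophil counts to neutropenia, and the second supplement repeats 5.9.7 with febrile neutropenia added.
- The first supplement defines Grade 3 or 4 neutrophil and lymphocyte decreases from laboratory values.
- SAP 5.9.8, 5.9.9 and 5.11 report actions and outcomes, and SAP 4.1 reports cycles received and reasons for stopping.

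These have limits. SAP 5.9.7 rests on reported events not judged unrelated. The first supplement uses its laboratory thresholds only to study infections. For AST/ALT and creatinine, laboratory grades are derived at baseline only; later abnormalities appear only if reported as adverse events.

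The sizes above can fairly be challenged. Nothing in the documents supports the assumed values, and a normal distribution with mean 4,000 and SD 2,000 puts about 2% of counts below zero. The protocol also mentions dose reduction and restart after interruption as ways of continuing treatment, and the stopping reasons in SAP 4.1 include treatment goal achieved, inadequate response and transfer.

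**Conclusion.** The point holds in a limited form. SAP 5.8.1 contains no measure of change within patients, and its columns describe different groups. Selective drop-out can therefore create, hide or reverse an apparent trend.

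The illustrative size is 6% to 13% of the mean under the first set of assumptions and 11% to 24% under the second. It is zero when drop-out is unrelated to the value. It would be tempting to conclude that the report will show false recovery of counts. The documents fix neither the size nor the direction, so that conclusion is not available.

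Neutropenia reported as a related event is adequately covered elsewhere. What is missing is the trend itself and, mainly for AST/ALT and creatinine, a laboratory-based view of the worst value reached. This is a worthwhile addition to a secondary descriptive output; it does not undermine the main safety tables.

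**What to change.** - **Paired change.** In SAP 5.8.1, at each time point, add the summary of within-patient change from baseline, with the number of patients having both values and the baseline mean of those same patients.
- **Shift table.** Add a table from baseline grade to worst post-baseline laboratory grade, using all post-baseline values rather than only the one selected per window. Do this for AST/ALT and creatinine, and for neutrophils as a laboratory-based complement to 5.9.7. The cut-offs are already in the definitions in SAP section 1. Patients who stop early are included if they have a baseline grade and any post-baseline value.
- **Reporting.** Keep the raw summaries and box plots, but base statements about change on the paired results. State that paired change reduces, and does not remove, the effect of selective drop-out.

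The cost is a few extra tables from data already collected. Patients with no baseline value will not appear in the change columns, though they remain in the raw summaries.

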## 7.0 Methods

### 7.1 Observation period

From the start of treatment with Adcetris until the completion of 16 cycles [3 weeks per cycle]

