###### 2) When to collect outcome measure data

At each test time point during the period from the start of treatment with Adcetris until the completion of 16 cycles (or upon discontinuation of treatment with Adcetris)

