1.1.2 Efficacy analysis set

In this survey, the efficacy analysis set is defined as patients treated with Adcetris IV Infusion with no major protocol violation and evaluable for efficacy.

Definition

Term	Definition
This/the product	Refers to Adcetris for intravenous drip infusion in this Statistical Analysis Plan.
SOC	MedDRA/J System Organ Class
HLGT	MedDRA/J High Level Group Term
PT	MedDRA/J Preferred Term
LLT	MedDRA/J Lowest Level Term
Patients registered	Patients whose registration has been approved
Patients whose case report forms are available	Patients whose case report forms have been collected
Patients whose case report forms are not available	Patients registered but whose case report form have not been collected
Fixed patients	Patients whose case report forms are available, with the date of case report form completion entered in the PMS system
Non-fixed patients	Patients whose case report forms are available, with the date of case report form completion not entered in the PMS system
Safety analysis set	Fixed patients included in the safety analysis set
Safety analysis set (Hodgkin's lymphoma)	Patients included in the safety analysis set whose diagnosis is Hodgkin's lymphoma
Safety analysis set (anaplastic large-cell lymphoma)	Patients included in the safety analysis set whose diagnosis is anaplastic large-cell lymphoma
Patients excluded from the safety analysis set	Fixed patients excluded from the safety analysis set
Efficacy analysis set	Patients included in the safety analysis set who are also included in the efficacy analysis set
Patients excluded from the efficacy analysis set	Patients included in the safety analysis set who are excluded from the efficacy analysis set
Patients completing treatment	Patients completing 16 cycles of treatment with Adcetris
Patients discontinuing treatment	Patients not completing 16 cycles of treatment with Adcetris

Term	Definition
Adverse drug reactions, etc.	
Refers to “adverse drug reactions and infections.”
 
Adverse events not considered “not related” to Adcetris by the investigator.
 
In this Statistical Analysis Plan, the term “adverse drug reactions and infections” is used in titles and the term “adverse drug reactions, etc.” is used in text and tables.

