4.0 Treatment Given

4.1 Treatment given

(1) Analysis sets to be used

Safety analysis set, safety analysis set (Hodgkin’s lymphoma), and safety analysis set (anaplastic large-cell lymphoma)

(2) Data to be analyzed

For each data item, patients will be stratified into the following categories below, and the frequency will be calculated. In addition, summary statistics of continuous variable will be calculated:

Data item	Category
Initial dose of Adcetris	<1.2 mg/kg, 1.2 mg/kg, >1.2 mg/kg to <1.8 mg/kg, 1.8 mg/kg, or >1.8 mg/kg
Mean dose of Adcetris	<1.2 mg/kg, 1.2 mg/kg, >1.2 mg/kg to <1.8 mg/kg, 1.8 mg/kg, or >1.8 mg/kg
Dose of Adcetris per 3 weeks	<1.2 mg/kg, 1.2 mg/kg, >1.2 mg/kg to <1.8 mg/kg, 1.8 mg/kg, or >1.8 mg/kg
Duration of treatment with Adcetris	1, 2, 3, 4, 5, 6, 7, 8, 9, 10, 11, 12, 13, 14, 15, 16, or ≥ 17 cycles
Reason(s) for discontinuation of Adcetris	Treatment goal achieved, adverse event(s), lost to follow-up, transfer to another hospital, pregnancy, inadequate response, and/or other
Post-baseline hematopoietic stem cell transplantation	Absent, present, or unknown
Type of post-baseline hematopoietic stem cell transplantation	Autologous or homologous
Days from the date of the last dose of Adcetris to hematopoietic stem cell transplantation (autologous) (Post-baseline hematopoietic stem cell transplantation: autologous)	-
Duration of treatment with Adcetris prior to	-

hematopoietic stem cell transplantation (autologous) (Post-baseline hematopoietic stem cell transplantation: autologous)	
Days from the date of the last dose of Adcetris to hematopoietic stem cell transplantation (homologous) (Post-baseline hematopoietic stem cell transplantation: homologous)	-
Duration of treatment with Adcetris prior to hematopoietic stem cell transplantation (homologous) (Post-baseline hematopoietic stem cell transplantation: homologous)	-
Drug(s) other than Adcetris used for the treatment of the primary disease	Absent or present
Drug(s) used for the prevention of infection	Absent or present
Specific drug(s) used for the prevention of infection	Antibiotics/synthetic antibacterial agents, antifungals, antivirals, trimethoprim-sulfamethoxazole combinations, and/or other prophylactics against infections

(3) Figure/table number

Tables 4.1-1 to 4.1-3

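### Laboratory windows and summaries in the final-analysis SAP stop on the day of the 16th dose, so later Cycle 16 values that the protocol collects are assigned to no time point

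*SAP*

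**What the plan says.** **Protocol.** Section 7.1 sets the observation period: "From the start of treatment with Adcetris until the completion of 16 cycles [3 weeks per cycle". Section 9.2.4.1 sets laboratory collection to match: "At each test time point during the period from the start of treatment with Adcetris until the completion of 16 cycles", or until discontinuation. Section 10.4.3 asks only for summary statistics at baseline and after baseline.

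**Final-analysis SAP.** Section 1.4 assigns each test value to a time point through a table of windows. The last row is After 15 cycles. It has two branches: "If Cycle 16 is initiated: From the day after the date of Cycle 15 to the day of Cycle 16" and "If Cycle 16 is not initiated: From the day after the date of Cycle 15 to 21 days after the date of Cycle 15". There is no row for 16 cycles, for a final assessment or for the last available value. Section 5.8.1 matches the table: summaries of twelve laboratory parameters "will be calculated at each test time point [at baseline, after 1 cycle, ... and after 15 cycles", with box plots of four of them at the same points.

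Elsewhere the same SAP goes further. Its definitions table has a group for "Patients completing 16 cycles of treatment with Adcetris", and the exposure categories in 4.1 end with "13, 14, 15, 16, or ≥ 17 cycles".

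**Supplemental SAP (September 2017).** Section 1.4 repeats the same window table, again ending at After 15 cycles.

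**The concern.** The by-cycle display leaves out the last cycle of the period over which the protocol collects laboratory data, and no reason is given.

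The cut does not fall evenly. The table's own rule gives a patient who stops early a window after the last dose. Patients who receive the 16th dose, the group with the longest exposure, get none after that day. Laboratory values at full cumulative exposure are therefore not shown for the patients who took the whole course, and follow-up after the last dose differs between them and patients who stopped sooner.

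The laboratory section is also out of step with the rest of the SAP. The adverse event tables in 5.2 have onset classes of 316 to 336 days and of 337 days or more, and 6.1 analyses best response after 16 cycles.

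**Working it through.** The plan states no figure to reproduce. The check maps the SAP 1.4 windows onto the nominal schedule.

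**Inputs**
- Cycle length of 21 days and 16 cycles (Protocol 7.1).
- The initial dose is day 1 (SAP 1.4).
- If the next cycle is given, the window runs from the day after the current dose to the day of the next dose. If not, it runs to 21 days after the current dose (SAP 1.4, rows for 2 to 15 cycles). The row for 1 cycle names a single day only.

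**Formula.** With no delays, dose k falls on day 1 + 21 × (k − 1).

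**Where the windows end**
- Dose 16: 1 + 21 × 15 = day 316. The last window closes here.
- 21 days after dose 16: 316 + 21 = day 337.
- Length of the observation period: 16 × 21 = 336 days, so counting day 1 as the first day it ends on day 336.

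**Coverage after the last dose**

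| Doses received | Day of last dose | Days covered after it |
|---|---|---|
| 1 | 1 | day 22 only |
| 2 | 22 | 23 to 43 |
| 14 | 274 | 275 to 295 |
| 15 | 295 | 296 to 316 |
| 16 | 316 | none |

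A patient with 17 or more doses likewise has no window after the day of dose 16, although for that patient dose 16 is not the last.

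**Size of the gap.** The uncovered days are 317 to 336 (20 days, 20/336 = 6.0%) or 317 to 337 (21 days, 21/336 = 6.25%), depending on whether the period is closed at day 336 or at 21 days after dose 16. Delays move these dates but do not close the gap, because the last window is tied to the actual date of Cycle 16.

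**Supplemental SAP 2.2.** Patients enter these analyses by either of two routes. One is a Grade 3 or 4 neutropenia or lymphopenia adverse event, which no laboratory window touches. The other is a count below 1,000/mm³ (neutrophils) or 500/mm³ (lymphocytes). Neither the definition of these counts nor Section 2.2 refers to Section 1.4. However, 1.4 opens with a general rule for handling test data, and that document plans no by-time-point laboratory table for which the windows would otherwise be needed. The text can be read either way.

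**The case against.** Four points can fairly be made for the plan.

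1. **Cycle 16 is not unobserved.** A reader might infer that a cytopenia or a liver or renal change after dose 16 would be invisible. The documents do not support that. Protocol Table 1 counts an abnormal laboratory finding as an adverse event, and 9.2.5 collects adverse events to completion of 16 cycles with the associated laboratory course. SAP 5.1.1 recodes count decreases to the matching cytopenia terms, and 5.2 tabulates onset up to and beyond day 336. This stands and limits the gap to values not reported as events and to the descriptive trend itself.

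2. **No planned analysis is breached.** A reader might take this as a departure from the protocol's analysis section. It is not, because 10.4.3 names no 16-cycle time point, and 5.8.1 has no test or decision attached. This stands too. The mismatch is with the collection period in 9.2.4.1.

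3. **The Supplemental SAP analyses may be untouched.** It would be too strong to say that Cycle 16 counts are lost from 2.2. At most the low-count route is affected, and only if 1.4 is read as governing it.

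4. **The day of dose 16 is included.** A sample from that day falls in After 15 cycles. The SAP does not say whether it is taken before or after the infusion, so the last displayed point cannot be called a pre-dose value. The gap concerns later days only.

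None of this explains why a by-cycle display should omit the final cycle, or why only patients reaching dose 16 should lose the follow-up window. Other SAP versions in the file contain a 16-cycle row; that is not evidence of error, and the point does not rest on it.

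**Conclusion.** The point holds as a gap in the descriptive laboratory analysis. Values collected after the day of dose 16 are assigned to no time point and drop out of 5.8.1, nominally about 20 or 21 of 336 days. They come from the patients with the longest exposure, while patients who stop after 2 to 15 doses keep a 21-day window.

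The day numbers assume 21-day cycles without delay; the gap itself does not. How much it matters depends on how many patients reach dose 16 and have a later sample in Cycle 16, and the documents give neither number. Adverse event reporting is unaffected. Supplemental SAP 2.2 is affected only on one reading of an ambiguous text. The consequence is modest, but the omission is unexplained and easily corrected.

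**What to change.** - **SAP 1.4 and Supplemental SAP 1.4:** add an After 16 cycles row. The window runs from the day after Cycle 16 to 21 days after Cycle 16, or to the date of Cycle 17 if that is earlier; the end of the window is the target date. The cap matters: following the table's existing pattern to a delayed Cycle 17 could carry the window past the protocol's collection period.
- **SAP 5.8.1:** extend the summaries and box plots to after 16 cycles.
- **Supplemental SAP 2.2:** state that every neutrophil and lymphocyte count in the observation period qualifies, whatever the Section 1.4 windows.

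The cost is one row in each window table, one further column for each of the twelve parameters and one further box for each of the four plotted, in each of the three analysis sets. The data are already collected under Protocol 9.2.4.1, so there is no added burden on patients or sites.
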